Appendix C. Insulin Infusion	109
Appendix D. Quality of Life Questionnaires.....	112

[figure not shown]
R477-202: Part A

Figure 1-1: Study Design Schema

R477-202: Part B

Figure 1-2: Study Design Schema

Study Glossary

Abbreviation or Term	Definition/Explanation
AE(s)	adverse event(s)
ADA	American Diabetes Association
ALP	alkaline phosphatase
ALT	alanine transaminase
ANC	absolute neutrophil count
AST	aspartate transaminase
AUC	area under the curve
BMI	body mass index
CGM	continuous glucose monitor
Cmax	maximum observed concentration
CMO	contract manufacturing organization
CRU	Clinical Research Unit
CSR	Clinical Study Report
CTCAE	common terminology criteria for adverse events
eCRF	electronic case report form
ECG	electrocardiogram
EOS	end of study
FFA	free fatty acid
FIH	first-in-human
FSH	follicle-stimulating hormone
GCGR	glucagon receptor
GCP	good clinical practices
GLP-1	glucagon-like peptide 1
HbA1c	hemoglobin A1c
HbsAg	hepatitis B surface antigen
HepC Ab	hepatitis C antibodies
HIV	human immunodeficiency virus
ICF	Informed Consent Form
IRB	institutional review board
LFT	liver function test
MEN	multiple endocrine neoplasia
MMTT	mixed meal tolerance test
MRI-PDFF	magnetic resonance imaging – proton density fat fraction
MRT	mean residence time
MTD	maximum tolerated dose
NOAEL	no observed adverse event level
OBV	overnight baseline visit
PD	Pharmacodynamic
PI	Principal Investigator
PK	Pharmacokinetic
QRS	QRS complex in ECG recording
QTc	QT interval (corrected)
REMD	REMD Biotherapeutics Inc.
REMD-477	A glucagon receptor antibody developed by REMD
SC	Subcutaneous
T1DM	Type 1 diabetes mellitus
ULN	upper limit of normal

1. OBJECTIVES

Primary Objective:

- To compare the effects of multiple doses of REMD-477 versus placebo on change from baseline at Week 12 in daily insulin requirements.

Secondary Objectives:

- To compare the effects of multiple doses of REMD-477 versus placebo on measures of glycemic control including change from baseline at Week 13 in fasting glucose and glucose AUC after MMTT – in Part A only.
- To compare the effects of a multiple doses of REMD-477 versus placebo on change from baseline at Week 12 in average daily 24-h blood glucose concentration and time within target range as assessed by continuous glucose monitoring (CGM) and seven-point glucose profile.
- To compare the effects of multiple doses of REMD-477 versus placebo on the product of the ratio of average glucose (Week 12/Baseline) and ratio of average insulin use (Week 12/Baseline).
- To evaluate the safety and tolerability of multiple doses of REMD-477 versus placebo.
- To compare the incidence of hypoglycemic episodes after multiple doses of REMD-477 versus placebo.
- To compare the effects of multiple doses of REMD-477 versus placebo on change from baseline at Week 13 in HbA1C.
- To compare the proportion of subjects who achieve HbA1c reduction of $\geq 0.4\%$ after multiple doses of REMD-477 versus placebo at Week 13.
- To compare the effects of multiple doses of REMD-477 versus placebo on pancreatic beta cell function as measured by change from baseline at Week 13 in C-peptide AUC after an MMTT and arginine challenge test (for a subset of subjects who were enrolled prior to Protocol Amendment #1) – in Part A only.
- To compare the effects of multiple doses of REMD-477 versus placebo on pancreatic alpha cell function as measured by change from baseline at Week 13 in peripheral levels of fasting glucagon, active and total glucagon-like peptide 1 (GLP-1), and glucagon and GLP-1 (active and total) AUC after MMTT – in Part A only.
- To determine REMD-477 plasma concentrations and formation of anti-REMD-477 antibodies after multiple dosing.

Exploratory Objectives:

- To compare the effects of multiple doses of REMD-477 versus placebo on change from baseline at Week 13 in body weight.
- To compare the effects of multiple doses of REMD477 versus placebo on change from baseline at week 13 in QOL score.
- To explore the effects of multiple doses of REMD-477 on the intrahepatic lipid content as measured by magnetic resonance imaging – proton density fat fraction (MRI-PDFF) (for a subset of subjects in Part B only)
- To explore the effects of multiple doses of REMD-477 on the intrahepatic lipid content as measured by Fibroscan® (for a subset of subjects in Part B only)

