For the product of the ratio of average glucose (Week 12/Baseline) and ratio of average insulin use (Week 12/Baseline), glucose AUC after MMTT, C-peptide AUC after MMTT and arginine challenge test (for a subset of subjects in Part A who were enrolled prior to Protocol Amendment #1), fasting glucose, insulin, C-peptide, GLP-1, and glucagon, a repeated measures analysis of covariance will be performed, as well as before and after treatment analysis.

For comparison of proportion of subjects that achieve HbA1c reduction of $\geq 0.4\%$ in the REMD-477 and placebo groups, chi-square test will be conducted.

For a subset of subjects in Part B, the change in hepatic fat content from baseline will be calculated for each subject and the mean change will be calculated for each treatment arm.

Study Disposition and Demographic Data

The number of subjects who receive investigational product and complete the study will be summarized. A list of subjects who withdraw early will be provided. It will include the reason and timing of the withdrawal. Similarly, the reason any subject is excluded from an analysis set will also be provided. In addition, significant known protocol deviations will be noted for individual subjects.

Age, race, sex, height, and weight will be summarized for all the subjects receiving investigational product using descriptive statistics.

Population Pharmacokinetics

Serum REMD-477 concentrations will be determined using a validated assay. A population

PK analysis will be performed from REMD-477 concentrations evaluated on Days 1, 8, 29, 57, 85, and 106.

Safety Analysis

Adverse Events

All subjects who receive at least one dose of REMD-477 or placebo will be included in the safety analyses. The number of subjects reporting treatment-emergent adverse events will be determined overall, by preferred term, and by system organ class according to the current MedDRA terminology. The number and percentage of subjects reporting adverse events will be evaluated for each treatment and will also be tabulated by relationship to study drug.

Adverse events resulting in treatment discontinuation will be identified.

Vital Signs

Vital signs will be listed and reviewed for each subject. Summaries of heart rate and blood pressure data over time and change from baseline will be provided. Depending on the size and scope of change in other vital signs, summaries may be provided for this data.

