10.3.4 Efficacy and Pharmacodynamic Statistical Methodology

10.3.4.1 General

All data, including derived parameters, will be listed and summarized for Part A and B separately. Absolute changes (and percentage changes, where applicable) from baseline will also be listed and summarized. Values outside the reference ranges will be flagged, if appropriate.

Preliminary analyses of variance will be performed to assess whether the baseline average daily insulin use and HbA1c levels among subjects are similar between the treatment groups. If any significant difference exists between any two treatments at the 5% level ($p \leq 0.05$), the variable will be used as a covariate in the repeated measures analysis of covariance (ANCOVA) as described in this section to adjust for any pre-intervention difference between treatment groups.

In all analyses, careful attention will be given to the appropriateness of the statistical procedure by determining whether necessary conditions are satisfied; e.g., normality and equal variance. When conditions are violated, the use of data transformations intended to produce data that satisfy normality and equal variance assumptions will be explored. If an appropriate transformation cannot be found, non-parametric methods may be used as an alternative to the more standard analyses.

For all repeated measures ANCOVA of efficacy and pharmacodynamic endpoints, the SAS codes used will be similar to the following:

```
proc mixed data=xxx;
class subject day treatment;
model variable = baseline subject treatment day treatment*day;
repeated day / subject=subject type=csh;
lsmeans treatment*day / pdiff cl alpha=0.05;
ods output lsmeans=lsm;
ods output diffs=diff;
run;
```

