10.3.4.6 HbA1c

The HbA1c concentrations will be summarized separately for Parts A and B by treatment group and timepoint, along with changes from baseline. The baseline assessment for Part A subjects is defined as the measurement taken at the Lead-In (OBV) period for those subjects enrolled prior to Amendment # 1 of the protocol or the baseline visit for those thereafter. For subjects enrolled in Part B the baseline assessment is defined as the last assessment taken prior to Day 1 dosing..

The changes from baseline for HbA1c will be statistical analyzed separately for Parts A and B. A repeated measures ANCOVA will be used to compare changes between treatment groups for each timepoint. Dependent variables will be treatment, day, and the treatment by day interaction. The baseline variable will be used as a covariate. Covariates may be added to the above model depending on the results from the comparison of baseline characteristics as detailed in section [10.3.4.1](#).

Subject will be used as a random effect. The LS mean for each treatment will be presented for each timepoint. Also, the difference from placebo, the 95% CI of the difference from placebo, and p-value associated with the null-hypothesis of no difference will be reported for each timepoint.

The number and proportion of subjects who achieve HbA1c reduction of $\geq 0.4\%$ will be summarized separately for Parts A and B by timepoint and treatment group. Reduction of $\geq 0.4\%$ is defined by the occurrence of a change from baseline which is less than -0.4% . A chi-square test will be conducted to compare the frequency observed in each of the two REMD-477 treatment groups versus the placebo group at each post-baseline timepoint.

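### The HbA1c responder comparison is not adjusted for baseline HbA1c; the chi-square is valid, but some precision may be lost and chance imbalance is left uncorrected

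*Protocol*

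**What the plan says.** The secondary objective in Protocol section 1 opens "To compare the proportion of subjects who achieve HbA1c reduction of" and sets the threshold at 0.4%; it names no test. SAP 10.3.4.6 sets the test: "A chi-square test will be conducted to compare the frequency observed in each of the two REMD-477 treatment groups versus the placebo group". The test is repeated at every visit after baseline with an HbA1c value, and no covariate or stratum is named. Protocol section 10 (Analysis of Key Study Endpoints) agrees: "in the REMD-477 and placebo groups, chi-square test will be conducted". A response, in the SAP, "is defined by the occurrence of a change from baseline which is less than" -0.4%, so the outcome is built on each subject's own change.

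For the continuous HbA1c change, the same SAP section says: "The baseline variable will be used as a covariate". That holds whether or not the arms differ at baseline.

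SAP 10.3.4.1 tests baseline insulin use and baseline HbA1c across arms. "If any significant difference exists between any two treatments at the 5% level", then "the variable will be used as a covariate in the repeated measures analysis of covariance (ANCOVA) as described in this section". The sections on the other modelled efficacy and pharmacodynamic endpoints refer back to this rule, including the single-timepoint ANOVA of the glucose-insulin product in 10.3.4.4. The sentences on the responder chi-square do not.

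SAP 10.1 produces outputs separately for Parts A and B. Protocol section 5 (Randomization) describes no stratification by HbA1c.

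**The concern.** Screening HbA1c may lie anywhere above 7% and below 10%. There is reason to expect the starting value to predict a fall of 0.4 points:

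- All subjects titrate insulin to the same glucose targets, so those who start higher have further to fall.
- In Part A, subjects at or below 8.0% at screening may have their insulin reduced on the day of randomization, which ties management to starting HbA1c.
- A change score carries the measurement error of its own baseline.

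If baseline is prognostic, a chance difference between two arms of 25 moves the responder difference in a known direction, and the planned test makes no use of that knowledge. Even an imbalance large enough to trigger the 10.3.4.1 rule would leave the responder test unchanged. The rule adds nothing to the continuous HbA1c model, which already contains baseline HbA1c, and it does not reach the one HbA1c analysis without it. An adjusted responder analysis added after unblinding would be open to the charge of being post hoc.

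**Working it through.** **The plan's own figure.** The only sizing is for daily insulin use (Protocol section 10, SAP section 8): CV 36%, difference 30%, power 0.8, alpha 0.05. Two-sided, n = 2 × (1.96 + 0.8416)² × (0.36/0.30)² = 22.6 per group. The stated figure is at least 22, with 25 enrolled, so it reproduces to within rounding. No responder rate or power is given for the HbA1c comparison.

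**Inputs.** From the documents: 25 per arm in each Part and the HbA1c entry range. Assumed, because the documents are silent: baseline SD about 0.7, slope of HbA1c change on baseline -0.2 to -0.5, residual SD 0.45 to 0.6.

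**Size of a chance imbalance.** The SE of the difference in mean baseline is 0.7 × √(2/25) = 0.198 points. With a t-multiplier of 2.01, only a gap of about 0.40 points would reach p ≤ 0.05 in the 10.3.4.1 check.

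**Shift in the responder difference.** A one-SE imbalance moves the difference in mean change by |slope| × 0.198. To first order the responder difference moves by that amount times φ(z)/s, where s = √(slope² × 0.7² + residual SD²) and φ(z) is the normal density at the responder cut.

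- Low end (slope -0.2, residual SD 0.6, 30% responders): s = √(0.14² + 0.6²) = 0.616; 0.0396 × 0.348/0.616 = 0.022.
- High end (slope -0.5, residual SD 0.45, 50% responders): s = √(0.35² + 0.45²) = 0.570; 0.099 × 0.399/0.570 = 0.069.

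The shift is therefore about 2 to 7 percentage points. For 30% versus 60% responders, the SE of the raw difference is √(0.3 × 0.7/25 + 0.6 × 0.4/25) = 0.134, so the shift is roughly 0.15 to 0.5 of one SE.

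**Power.** Simulation of 25 versus 25, 15,000 trials per row, with residual SD 0.55, placebo mean change -0.1 and drug effect -0.5. The comparison is the chi-square against a logistic likelihood-ratio test with baseline HbA1c. The last row extends the slope beyond the assumed range.

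| Slope | Correlation of change with baseline | Chi-square | Adjusted |
|---|---|---|---|
| -0.2 | -0.25 | 73.0% | 71.5% |
| -0.3 | -0.36 | 70.4% | 70.7% |
| -0.4 | -0.45 | 66.3% | 68.5% |
| -0.5 | -0.54 | 61.7% | 66.6% |
| -0.6 | -0.61 | 56.7% | 64.7% |

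A second set (30% versus 60% responders, residual SD 0.6, 8,000 trials each) gave 61.8% vs 60.4% at slope -0.2, 62.3% vs 62.4% at -0.35, and 61.2% vs 64.8% at -0.5. With residual SD 0.45 and slope -0.5 the gain was about 8 points. The change in power is thus roughly -1 to +8 points.

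**Precision.** Over slopes -0.2 to -0.5 and residual SD 0.45 to 0.6, the standardised risk difference had an SD of 0.119 to 0.135, against 0.133 to 0.135 for the raw difference.

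**Type I error.** In the first simulation set the chi-square rejected 5.3% to 5.6% of null trials overall, but 6% to 13% of those with an imbalance above 1.5 SE in either direction. Under the assumed drug effect, its power was 82% to 86% when imbalance favoured drug by more than one SE. It fell from 62% to 27%, as the slope steepened, when imbalance ran against drug by more than one SE. The likelihood-ratio test was slightly liberal, at up to about 6.4% at the steepest slope with 30% versus 60% responders assumed.

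**The case against.** An unadjusted chi-square is a conventional and valid choice for an unpowered secondary responder endpoint in phase 2. Randomisation protects it on average, and a shift of 2 to 7 points is part of the sampling error that its 13-point SE already reflects. No confirmatory claim depends on it, because the Hochberg sequence is specified only for daily insulin use. The more informative continuous HbA1c endpoint is adjusted for baseline in every case. The SAP Introduction also permits supplementary analyses identified in the study report. All of this stands and limits the weight of the point. It does not remove it: an analysis added later is not pre-specified, and the standardised difference was never less precise than the raw one in the scenarios run.

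A reader might go further and infer three things that the documents do not support:

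- **That the test is invalid or its error rate inflated.** Overall type I error is close to 5%; only the rate conditional on a large imbalance rises.
- **That baseline is ignored.** The response is itself a change from baseline. What is missing is adjustment for the starting level.
- **That power is certainly lost.** This depends on a baseline-to-response relationship that the documents do not give. At weak correlation adjustment gains nothing or loses about a point, and part of any apparent gain reflects the slightly liberal likelihood-ratio test.

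Disagreement between the two HbA1c analyses would also prove little, since a dichotomised and a continuous analysis can differ for other reasons.

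**Conclusion.** The point holds as a minor one. The responder chi-square is unadjusted at about 25 versus 25, and the imbalance rule does not reach it, although baseline HbA1c is one of only two variables that the SAP screens for imbalance. What is at stake is the precision of the responder difference and its bias given the imbalance that actually occurs. The size rests wholly on the assumed SDs and slopes; a weakly prognostic baseline puts it at the bottom of the ranges shown. The primary endpoint and its sample size are unaffected. This would be nice to have and is not required.

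**What to change.** In SAP 10.3.4.6, before database lock:

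- Make the Week 13 responder comparison, within each Part, a logistic regression on treatment and baseline HbA1c.
- Report the baseline-standardised risk difference for each dose versus placebo with a 95% CI, and name the interval method (for example delta method or bootstrap).
- State a fallback if the model separates, such as Firth penalisation.
- Keep the chi-square as a supporting analysis.

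The cost is a short paragraph and modest programming; baseline HbA1c is already collected. The change also supplies an effect estimate and interval, which the section does not now specify for this endpoint. The downsides are little or no gain if baseline is weakly prognostic, and a likelihood-ratio test that is slightly liberal at this sample size.

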2. BACKGROUND AND RATIONALE

Type 1 Diabetes

Diabetes is a growing health concern worldwide. Globally, as of 2010, an estimated 285 million people had diabetes, with type 1 making up about 10% of the cases ([Williams textbook of endocrinology 12th edition](#)). In 2013, an estimated 381 million people globally had diabetes (Int Diab Federation, 2015). By 2030, this number is estimated to almost double ([Wild, 2004](#)). In 2012, 29.1 million Americans, or 9.3% of the population, had diabetes, and approximately 1.25 million American children and adults have type 1 diabetes ([National Diabetes Statistics Report, 2014](#)).

Type 1 diabetes mellitus (previously known as insulin-dependent, juvenile or childhood-onset) results from autoimmune destruction of the insulin-producing beta cells in the pancreas. The subsequent lack of insulin leads to increased blood and urine glucose. The classical symptoms are polyuria (frequent urination), polydipsia (increased thirst), polyphagia (increased hunger) and weight loss ([Cooke, 2008](#)). Type 1 diabetic patients rely on insulin injections to control blood glucose.

Optimal blood glucose control in T1DM requires insulin in amounts that far exceed the endogenous insulin secreted by normal β -cells ([Unger, 2010](#); [Wang, 2013](#)). A recent large scale observational study in 33,915 patients with T1DM, based on the Swedish National Diabetes Register (data of Jan 1998 - Dec 2011), showed that insulin treated T1DM patients had a significantly elevated risk of death due to cardiovascular diseases (death rate 2.7% vs. 0.9%) in comparison to the age-, sex-, and county-matched controls from the general public ([Lind, 2014](#)). Even among patients with better glycemic control (glycated hemoglobin $\leq 6.9\%$) and reduced diabetes-related death, there is still a nearly two-fold increase (1.7% vs. 0.9%) in cardiovascular disease related death, in comparison to the general public controls. Other studies reported 6-10 fold greater mortality related to coronary heart disease (CHD) in T1DM patients ([Dorman, 1984](#); [Korlewski, 1987](#)). Two more studies, the Pittsburgh Epidemiology of Diabetes Complications (EDC) Study ([Orchard, 2003](#)) and Eurodiab Study ([Soedamah-Muthus, 2004](#)), confirmed significant increases in the Coronary Artery Disease (CAD)-related mortality in T1DM. Hyperinsulinemia is known to increase hepatic cholesterol and triglyceride synthesis through insulin-mediated up regulation of lipogenic and cholesterogenic transcription factors such as SREBP and enzymes ([Brown, 2008](#)), contributing to CAD or CHD.

Relative or absolute insulin excess is also associated with a prominent risk of hypoglycemia and sudden death in T1DM patients. Hypoglycemia is a common side effect of insulin therapy, and a fact of daily life, for people with T1DM ([Cryer, 2010](#)). The current clinical guidelines call for tighter glycemic control, to prevent diabetic complications, but such practice is associated with higher incidence of iatrogenic hyperinsulinemia and hypoglycemia. T1DM patients also suffer asymptomatic hypoglycemia. In one study of T1DM patients with subcutaneous glucose sensing, glucose levels were below 70 mg/dL for 1.5 hours per day, i.e., 6.3% of the time ([Beck, 2009](#)). In another study of nocturnal plasma glucose measurements every 15 minutes, hypoglycemia (glucose <70 mg/dL) was found in 57% (12 of 21) of the T1DM patients ([Raju, 2006](#)). Asymptomatic hypoglycemic episodes are not benign as they desensitize and impair the physiological defenses against subsequent hypoglycemia ([Cryer, 2010](#)). People with T1DM suffer an average of two episodes of symptomatic hypoglycemia per week, and thousands of such attacks over a lifetime of diabetes. They also suffer an average of one severe episode of temporarily disabling hypoglycemia per year, which can be life-threatening.

Glucagon Receptor Pathway in Type 1 Diabetes

Glucagon is the primary counter-regulatory hormone that opposes insulin action. Normal β -cells secrete insulin, which restrains glucagon release from the juxtaposed α -cells. However, in absence of intra-islet insulin, such as the case of type 1 diabetes, α -cells are unrestrained and glucagon secretion is unopposed. Data from a series of studies have demonstrated that an increase in glucagon in patients with type 1 diabetes is a key component of the pathogenesis of hyperglycemia; 1) hyperglucagonemia is a prominent feature of both type 1 and 2 diabetes; 2) glucagon increases circulating glucose levels by stimulating hepatic gluconeogenesis and glycogenolysis; 3) the glucagon suppressors, leptin and somatostatin, can suppress all catabolic manifestations of diabetes during total insulin deficiency; 4) total β -cell destruction fails to induce diabetes in glucagon receptor (GGR) knockout mice; and 5) perfusion of normal pancreas with anti-insulin antisera causes marked hyperglucagonemia ([Unger, 2012](#)). Recently, treatment with a glucagon receptor antagonist in a rodent model of T1D ([Zhi, 2013](#)) and in patients with T1D ([Garhyan, 2013](#)) found this therapy decreased insulin requirements.

Lack of insulin also leads to an unrestrained action of glucagon on the liver, which in turn unleashes the full capacity of the liver in glucose output and in ketone production. It has been reported that in insulin deficient animal models of diabetes, the metabolic

manifestations of insulin deficiency will not occur after GCGR knockout ([Lee, 2012](#)), and that insulin-deficient diabetes induced by streptozotocin injection, presented with severe hyperglycemia (>500 mg/dL), hyperketonemia, and fatal cachexia, can be prevented by GCGR knockout in mice ([Lee, 2011](#)).

It should also be noted that in clinical practice of treating T1DM, the exogenous insulin treatment can only attain the intra-islet insulin concentration at a small fraction of that achieved by the endogenous insulin. Therefore, glucagon hypersecretion and hyperactivity in T1DM cannot be adequately controlled by the exogenous insulin injections ([Unger, 2012](#)). These conditions predispose the type 1 diabetic patients to a metabolically vulnerable state, subjecting to poor diabetic control and risk of ketoacidosis.

The glucagon pathway has been contemplated as a therapeutic target in recent years. There have been some efforts in developing glucagon antagonists, including antibodies, but with little success even in preclinical settings. Antagonism to the GCGR is also being sought as a potential target, with small molecular antagonists being developed by a few pharmaceutical companies ([Kazda, 2014](#); [Vajda, 2014](#); [Petersen, 2001](#)).

While insulin remains a primary treatment for type 1 diabetes, its clinical utility and benefits are undermined by the undesirable iatrogenic hyperinsulinemia with associated cardiovascular and hypoglycemic complications. It is highly desirable to develop a safe and effective adjunct therapy that can substantially reduce the daily insulin doses. In contrast to the treatment of type 2 diabetes using a big range of therapeutic strategies, the treatment of type 1 diabetes places a heavy reliance on insulin with few choices for alternatives or add-ons. An effective and safe therapeutic alternative is badly needed to supplement and reduce insulin daily doses. This will substantially improve the diabetic control and life quality of the type 1 diabetic patients, and minimize iatrogenic hyperinsulinemia and hypoglycemia.

REMD-477 Background

Pharmacology

REMD-477 is a fully human IgG2 monoclonal antibody that binds to the human GCGR and antagonizes the effects of glucagon. In cell-based functional assays using recombinantly expressed glucagon receptors from various species, including human, mouse, rat, and cynomolgus monkey, REMD-477 blocks glucagon-induced cellular response (as measured by changes in cyclic AMP [cAMP] levels).

Both acute and chronic in vivo studies have been conducted with GCGR antibodies in normal mice, insulin-resistant diet-induced obesity (DIO) mice, and leptin-deficient *ob/ob* mice. Administration of GCGR antibodies lowered blood glucose in a dose-dependent fashion without inducing hypoglycemia in normal, DIO, and *ob/ob* mice. In a study conducted in normal cynomolgus monkeys, a single SC injection of the REMD-477 analog, 2-59.1, resulted in improved glucose tolerance as well as increased glucagon and GLP-1 levels. In the streptozotocin-induced T1DM model in mice, REMD2.59C (an REMD-477 analog) treatment totally corrected severe hyperglycemia (~500 mg/dL) after just the first weekly dose, normalized the HbA1c level to < 5%, and increased insulin immunostaining area in the islets, after 12 weekly doses of REMD-477 ([Pharmaron, 2014](#)). In another T1DM model induced by alloxan-injection in mice, an analog of REMD-477 (mAb Ac) corrected hyperglycemia after the 1st weekly injection, and normalized phosphorylated cAMP response element binding protein (p-CREB), a transducer of the glucagon signal, and suppressed phosphoenolpyruvate carboxykinase (PEPCK), a key enzyme in gluconeogenesis ([Wang, 2015](#)).

In chronic rodent studies, the chimeric murine GCGR neutralizing antibody GR15c was used as a surrogate to assess the effects of blocking the glucagon pathway on hyperglucagonemia, alpha cell hyperplasia, and beta cell function. GR15c treatment caused dose-dependent hyperglucagonemia and minimal to mild alpha cell hyperplasia due to adaptive compensation for the reduced GCGR signal. There was no evidence in these studies of pancreatic alpha cell neoplastic transformation in mice treated with GR15c for as long as 18 weeks. Both treatment-induced hyperglucagonemia and alpha cell hyperplasia were reversible after treatment withdrawal for periods of 6 and 10 weeks. Importantly, pancreatic beta cell function was preserved, as demonstrated by improved glucose tolerance throughout the 18-week treatment period.

Preclinical Studies

Preclinical Pharmacokinetics

The PK of REMD-477 exhibited dose-dependent nonlinearity in mice, rats, and monkeys, as demonstrated by the decrease in clearance values and the more than dose- proportional increases in exposure (as assessed by C_{max} and AUC_{0-t}) with increasing doses over the 1- to 10-mg/kg dose range in mice and rats and over the 0.1- to 1-mg/kg dose range in monkeys. Limited extravascular distribution of REMD-477 was observed across species.

Upon multiple dosing of REMD-477, no marked accumulation was observed in monkeys following weekly subcutaneous (SC) dosing for 2 weeks, 4 weeks and 12 weeks, while minimal to moderate accumulation was observed by the 4th dose and 12th dose in rats following weekly SC dosing for 4 and 12 weeks, respectively.

The detection of anti-REMD-477 antibodies was associated with lower serum REMD-477 exposure in most of the animals from both PK and toxicology studies that developed antibodies.

Preclinical Toxicology

A comprehensive program of toxicology studies with REMD-477 has been conducted to support the clinical development of REMD-477. REMD-477 is pharmacologically active in rats and monkeys, making both appropriate species for nonclinical safety assessment of this monoclonal antibody. The program consisted of 2-week exploratory subcutaneous toxicity studies in rats, rabbits and monkeys (3, 30, and 300 mg/kg/dose for both studies), a 1-month subcutaneous toxicity study in rats (1, 30, 300 mg/kg/dose), a 1-month subcutaneous and intravenous toxicity study in monkeys, (3, 30, 300 mg/kg/dose), 3- month subcutaneous toxicity studies in rats (3, 30, and 300 mg/kg/dose) and monkeys (30, 100, and 300 mg/kg/dose), and a tissue cross-reactivity study. The 2-week study in rats and the 1-month studies included recovery periods of 6 weeks and 3 months, respectively, and the 3-month studies included 6-month recovery periods. Effects after a single dose of REMD-477 were assessed in neurobehavioral and respiratory safety pharmacology studies in rats, and local tolerance was assessed in the repeated-dose studies in rats and monkeys.

The acute toxicity potential of REMD-477, as assessed in safety pharmacology studies in male rats, appears to be low. The only effects observed on toxicity parameters after a single dose were decreases in body weight gain and food consumption that are considered to be mechanism-based effects of REMD-477, i.e., secondary to increases in plasma GLP-1. The effects on body weight and food consumption were not considered adverse. Furthermore, there are no adverse effects on neurobehavioral or respiratory parameters. Therefore, the NOAEL in these single dose studies was 300 mg/kg.

REMD-477 caused mechanism-based changes in subcutaneous toxicity studies in rats of up to 3-months in duration. Treatment-related changes included decreases in body weight gain and food consumption, increases in plasma glucagon and GLP-1, and hyperplasia of

pancreatic islet alpha cells. The 3-month recovery period following the 3-month treatment study in rats demonstrated full to partial reversal of all effects. None of the treatment-related changes were considered adverse. The NOAEL in rats after 3-months of weekly subcutaneous injections was 300 mg/kg/dose, the highest dose tested.

REMD-477 was also well tolerated in toxicity studies in monkeys in toxicity studies of up to 3-months in duration. As in the rat, all of the changes were considered secondary to blockade of the glucagon receptor. Decreases in food consumption and body weight were observed at the highest dose level tested (300 mg/kg). Increases in plasma GLP-1 were observed in monkeys, but a clear effect on plasma glucagon was not demonstrated. Treatment-related changes in the pancreas consisted of hypertrophy of pancreatic islet cells and decreased glucagon-immunolabeling. All of the changes observed in the 1-month study reversed completely during the 3-month recovery period. The NOAEL in monkeys after 3-months of subcutaneous injections was 300 mg/kg/dose, the highest dose tested.

Serum glucose levels were not meaningfully altered by treatment of rats or monkeys with REMD-477. A marked increase in plasma glucagon was observed in rats but not monkeys. Neither plasma insulin nor pancreatic insulin immunolabeling were altered by REMD-477 in either rats or monkeys.

Pancreatic alpha cell hyperplasia is an expected consequence of blockade of the glucagon receptor in rodents, and, as expected, REMD-477 caused alpha cell hyperplasia in toxicity studies in rats. Full to partial reversal of the alpha cell hyperplasia was demonstrated in rodent pharmacology and toxicology studies. In monkeys, hypertrophy, but not hyperplasia, of islet cells was observed and was also reversible.

REMD-477 caused minor inflammatory reactions at the subcutaneous injection site in some of the rat and monkey studies.

REMD-477 was immunogenic in both rats and monkeys. Some of the anti-REMD-477 antibodies decreased systemic exposure to REMD-477 and/or neutralized its activity. The development of these antibodies did not confound the interpretation of the toxicity studies since sufficient numbers of animals did not develop anti-REMD-477 antibodies, and, of those that did, a proportion developed changes characteristic of treatment with REMD-477. The development of anti-REMD-477 antibodies in animals is not necessarily relevant to the clinical use of REMD-477, since animal models cannot be solely used to predict the immunogenicity of fully human proteins in humans. Furthermore, since REMD-477 is not an

endogenous protein, the potential safety issues associated with neutralizing an endogenous protein's activity are diminished for this molecule.

Results of a tissue cross-reactivity study showed that binding of REMD-477 to normal tissues was similar between humans, cynomolgus monkeys, and Sprague-Dawley rats.

In summary, results of the nonclinical safety program for REMD-477 has defined a favorable safety profile for the molecule. In safety pharmacology studies in rats, REMD-477 did not cause adverse neurobehavioral or respiratory effects. There were no treatment-related cardiovascular effects in the toxicity studies in monkeys. No adverse effects were observed in toxicity studies of up to 12 weeks in duration in rats and monkeys that were conducted at doses up to 300 mg/kg. All treatment-related changes in these studies, except for minor inflammation at subcutaneous injection sites, were considered secondary to glucagon receptor blockade. Significant safety margins to proposed clinical doses exist. The nonclinical safety data for REMD-477 support clinical trials in humans of up to 12 weeks in duration.

Clinical Studies

FIH Study 20060310

In the first-in-human (FIH) study (Amgen Study 20060310) in healthy volunteers, 56 healthy adult subjects were planned to receive a single dose of placebo or REMD-477 at the following doses: 0.3, 1, 2.5, 5, and 10 mg/kg SC or 0.3 and 5 mg/kg IV. Forty (40) subjects (30 active: 10 placebo) received a single 0.3, 1, and 2.5 mg/kg SC dose, or a single 0.3 mg/kg IV dose of REMD-477. 38 subjects completed the study, but 2 subjects withdrew consent; one subject failed to return to follow up visits as instructed and another subject voluntarily withdrew consent.

A total of 30 normal volunteers received a single dose of REMD-477 at 0.3, 1 or 2.5 mg/kg SC, or 0.3 mg/kg IV. There appears to be no significant drug related adverse events. No deaths, dose limiting toxicities or withdrawals due to adverse events have been reported. No notable changes in ECG, safety lab tests (aside from the elevated AST/ALT noted below) or vital signs were reported. No hypoglycemia was observed across all dose cohorts.

All subjects in the FIH trial tested negative for the development of anti-REMD-477 antibodies.

Overall in this study, adverse events were reported for 17 of the 30 subjects (57%) who

received AMG477, and for 5 of the 10 subjects (50%) who received placebo.

Adverse events reported for more than 2 subjects were muscle strain for 3 subjects (REMD-477, 3/30 = 10%); and pharyngolaryngeal pain for 3 subjects (REMD-477, 2/30 = 7%; placebo, 1/10 = 10%). All adverse events were reported as mild or moderate in severity, with the exception of an event of ingrowing nail for a subject in the AMG 477 0.3-mg/kg IV group that was reported as severe. Adverse events were reported as treatment related for 6 of the 30 subjects (20%) who received REMD-477 at any dose, and for 1 of the 10 subjects (10%) who received placebo. Adverse events reported as treatment related for two or more subjects were increased alanine aminotransferase (ALT) for 2 subjects (REMD-477, 2/30 = 7%); asthenia for 2 subjects (REMD-477, 1/30 = 3%; placebo, 1/10 = 10%); and dizziness for 2 subjects (REMD-477, 2/30 = 7%). All adverse events reported as treatment related were also reported as mild or moderate in severity.

